#### 5.7 Contact Force (CF) Settings

Operators should select individualized CF target ranges based on their case experience and the prior results from the THERMOCOOL SMARTTOUCH® SF catheter IDE trial.

- Contact Force settings:
  - Contact Force Target range: 5-25 gram (recommended)
  - Minimum CF of 3-5 grams
- Risk of cardiac tamponade and perforation may correlate with higher CF ( $\geq$  40 g) used during RF ablation.
  - For  $CF \ge 20g$ , power should be  $\le 35$  watts.
- Contact force data and individual procedure working ranges will be collected for each RF application during a study ablation procedure for offline analysis.

## 5.8 VISITAG™ Settings

- Stability Settings:
  - Range: 2-3 mm
  - Time: 3-5 seconds

- Filter (FOT) Settings:
  - $\circ~$  If an FOT filter is desired, the percentage of time of the chosen gram force should be 25%.
- Tag size 3mm
- Maximum Inter tag distance 6mm

## 5.9 VISITAG SURPOINT™ Tag Index Targets

VISITAG SURPOINT™ Module Tag Index target values for specified anatomical locations:

- Anterior, Ridge, Roof segments target value: 550
- Posterior and inferior segments target value: 380

**NOTE 1**: All Tag Index target values, especially the posterior wall, are in the absence of safety concerns (i.e. no temperature rise from esophageal probe, pain during conscious sedation or steam pop, etc). In the absence of safety concerns, achieveing target Tag Index values will be the endpoint of RF energy application.

**NOTE 2**: If for safety reasons the ablation needs to be stopped prior to reaching the Tag Index target value, please do so and document accordingly with associated VISITAGTM location number.

**NOTE 3**: Increases in power and force from previous workflow to hit a specific Tag Index target with a shorter procedure time is not recommended

#### **5.10 Ablation Procedure**

The ablation procedure includes PVI, ablation of non-PV triggers and substrate modification. Study procedure requirements are outlined below:

- PVI of all PV's are required (acute success)
- Linear ablation lines are only required to treat documented macro-reentry atrial tachycardia's and limited to the following targets only:
  - LA roof line
  - MV isthmus line
  - LA floor line
  - o CTI
- A right atrial CTI linear ablation is REQUIRED in cases with documented typical atrial flutter either prior to or during the procedure.
- Ablation of spontaneous non-PV triggers
- CFAE ablation (left atrial, right atrial and CS) is not recommended
- Ablation of non-PV triggers induced by adenosine or isoproterenol

**NOTE 4:** Tag Index target values for non-PV targets are not provided. The operator should follow the catheter IFU, use clinical judgment and their standard of care while ablating non-PV targets.

## Prophylactic ablation of empirical sites is not allowed.

All linear lesions require confirmation of bidirectional conduction block by pacing and/or mapping maneuvers.

#### 5.11 Post Ablation

- Verification of entrance block is required for all PVs.
  - A 30-minute waiting period is REQUIRED from the last RF application at a PV before verification may be confirmed. If reconduction is noted, additional RF applications should be applied and a second 30-minute waiting period will be required to recheck for entrance block. If reconduction is still noted, additional RF applications may be applied but a third 30-minute waiting period is not required prior to recheck for entrance block.
- To verify entrance block, analyze electrograms in sinus and/or atrial paced rhythm to confirm that no PV potentials are present.
  - Administration of adenosine or isoproterenol after a 30-minute waiting period is **REQUIRED** to rule out dormant conduction.
- Demonstration of entrance block MUST be confirmed and documented by the LASSO® Circular Mapping Catheter or PENTARAY® NAV Catheter.
- Linear ablation lines may only be performed to treat documented macro-reentry atrial tachycardia's (LA roof line, MV isthmus line, LA floor line, CTI.
  - o Bidirectional block must be confirmed and documented
- The ablation procedure is considered complete when confirmation of block is confirmed and documented.
- In addition to the data collected on the CRFs, a CARTO® backup file identified with the subject's study number will be made for each case and sent to the sponsor as part of the data collection.

#### **5.12 Post Procedure Assessments**

- Before hospital discharge:
  - Occurrence of arrhythmias, if any
  - Electrocardiogram (12-Lead ECG)
  - Transthoracic Echocardiogram (TTE), if necessary. Subjects who develop symptoms suggestive of pericardial effusion and/or pericarditis should undergo a transthoracic echocardiogram (TTE) to assess the pericardium, before hospital discharge. In the event significant pericardial effusion is identified, subjects should be followed until the condition resolves.

- Cardiac-related concomitant medications (such as AADs, anticoagulation regimen, etc.)
- Adverse events, if any
- Collect Subject Hospitalization Billing information (including UB04 and EOB)
- Follow-up measurements at 7-9 Days (telephone)
  - Medical History any change from previous
  - Occurrence of arrhythmias, if any
  - Cardiac-related concomitant medications (such as AADs, anticoagulation regimen, etc.)
  - o Adverse events, if any
    - Subjects who have symptoms suggestive of PV stenosis should undergo imaging (CT/MRI)
  - Health Economic Data for hospitalizations, ER visits and outpatient visits, if any
    - At all visits, health economic data to be collected may include, but is not limited to: hospitalization charge (UB04), repeat ablation procedure and/or procedures resulting from the ablation procedure, outpatient visits, and ER visits

## • Follow-up measurements at 1-Month (+/-7days):

- Medical history- any change from previous
- Physical Exam including standardized neurological assessment and cardiovascular/ pulmonary examination.
- Occurrence of arrhythmias, if any
- Electrocardiogram (12-Lead ECG)
- Concomitant medications only cardiac related (AADs, anticoagulation regimen, etc.)
- TTM Monitor (refer to section 5.16 for transmission schedules)
- Adverse events, if any
  - Subjects who have symptoms suggestive of PV Stenosis should undergo imaging (CT/MRI)
- Health Economic Data for hospitalizations, ER visits and outpatient visits, if any
  - At each follow-up visit, health economic data to be collected may include, but is not limited to: hospitalization charge (UB04), repeat ablation procedure and/or procedures resulting from the ablation procedure, outpatient visits, and ER visits

- Follow-up measurements at, 3-Month (+/- 7 days), 6 (+/-14 days), 12-Month (+/- 28 days) and Unscheduled Clinic Visits:
  - Medical History any change from previousOccurrence of arrhythmias, if any
  - Occurrence of arrhythmias, if any
  - Electrocardiogram (12-Lead ECG)
  - QOL Assessments (SF-12 Health Survey) (Only collected at 3, 6 and 12 months visit)
  - TTM Monitor (refer to section 5.16 for transmission schedules)
  - 24 hour Holter monitoring (12-month visit)
  - Concomitant medications only cardiac related (AADs, anticoagulation regimen, etc.)
  - Adverse events, if any
    - Subjects who have symptoms suggestive of PV Stenosis should undergo imaging (CT/MRI)
  - Health Economic Data for hospitalizations, ER visits and outpatient visits, if any
    - At each follow-up visit, health economic data to be collected may include, but is not limited to: hospitalization charge (UB04), repeat ablation procedure and/or procedures resulting from the ablation procedure, outpatient visits, and ER visits
  - End of Study Report Subject completion/discontinuation form (12-Month or last completed visit)

Note: For follow-up visit schedules defined in this protocol, 1 month = 30 days, 1 week = 7 days.

## 5.13 Standard Tests and Procedures

The required schedule for subject treatments and evaluations is summarized in Table 5-1.

	Pre-Procedure				Phone Call	Follow-Up Visits				
	Scree Base		Ablation Procedure 	Discharge	7-9 Days	1 Month +/- 1 wks	3 Month +/- 1 wks	6 Month +/- 2 wks	12 Month +/- 4 wks	Unsched uled Visit
Visit no.	1	2	3	4	5	6	7	8	9	10
Informed consent 	Х									
Inclusion & exclusion criteria	Х									
Demographics	Х									
Medical history	Х				$X^{10}$	X 	X 	$X^{10}$	X 	$X^{10}$
Physical Exam						Х				
Arrhythmias	X [history]			Х	Х	X	Х	Х	X	Х
ECG		Х		Х		Х	Х	Х	Х	Х
NYHA		Х								
QOL assessment 		Х					Х	Х	Х	
Pregnancy test 		Х								
LA thrombus Imaging 			X 							
TTE 		X 		X 						
Ablation assessments			Х							
Device deficiency			Х							
Concomitant medications 		Х	X	X	Х	X	X	X	X	Х
Health Economic Data Collection 				X 	X 	X 	X 	X 	X 	X 
Adverse events 	Х	Х	Х	Х	Х	Х	Х	Х	Х	Х

Table 5-1Schedule of Treatments and Evaluations

	Pre-Procedure				Phone Follow-Up Visits Call					
		ening / eline	Ablation Procedure 	Discharge	7-9 Days	1 Month +/- 1 wks	3 Month +/- 1 wks	6 Month +/- 2 wks	12 Month +/- 4 wks	Unsched uled Visit
Visit no.	1	2	3	4	5	6	7	8	9	10
TTM monitoring 						X 	X 	X 	X 	
24 Hour Holter									Х	
PV stenosis imaging assessment 					X 	X 	X 	X 	X 	X 
Subject Completion/ discontinuation form									X 	

-  Initial ablation procedure should be done within 30 days of consent.
-  Quality of life tools (SF-12 Health Survey)
-  Pregnancy test must be done on pre-menopausal women only, within 24 hours of the procedure.
-  Section 5.3 of the protocol should be followed when determining if a subject should undergo imaging for the presence of LA Thrombus.
-  Imaging TTE to determine the atrial size (if the subject has undergone an imaging procedure within the last 6-months where the atrial size was assessed, the pre-procedure imaging assessment is not required)
-  Concomitant medications: only cardiac related (anti-arrhythmia drugs, anticoagulation regimen, etc.)
-  Health Economic Data for hospitalizations (UB04), ER visits and outpatient visits, if any

-  AEs collected once consent has been signed
-  If AE results in Hospitalization health economic data collection is required
-  Collected to confirm no changes in medical history since last visit
-  TTM: all symptomatic cardiac episodes should be recorded and transmitted at the time the event occurs. Asymptomatic transmissions should be recorded as scheduled (weekly: months 2-5 and monthly: months 6, 7, 8, 9, 10, 11, 12) and transmitted to the Core Lab. Refer to section 5.16.
-  PV imaging (CT/MRI) for subjects who have symptoms suggestive of PV stenosis
-  Subjects who develop symptoms suggestive of pericardial effusion and/or pericarditis should undergo a transthoracic echocardiogram (TTE) to assess the pericardium
-  12-month visit or last completed visit

#### 5.14 Study Medications

The following medications are recommended/required (as indicated) for subjects undergoing a Study procedure ablation for AF.

#### 5.14.1 Anticoagulation Medications

#### • Medication Prior to AF Ablation Procedure

• Subject should be placed on systemic anticoagulation therapy for at least 3 weeks prior to the AF ablation procedure.

#### • Medication During AF Ablation Procedure

- **Heparin**: to achieve an activated clotting time (ACT) of  $\geq$  325 seconds during the AF ablation procedure in the left atrium.
- ACT levels MUST be checked prior to administering RF energy and rechecked every 15-30 minutes during the ablation procedure in the left atrium to ensure ACT ≥ 325 seconds. All recordings must be documented in the medical records as source documentation.
- Adenosine: 12 mg to 24 mg bolus to confirm PV isolation; rule out dormant conduction
- **Isoproterenol**: recommended if pacing maneuvers are not performed, to achieve a  $\geq 20$  beats per minute increase in heart rate to induce AF upon completion of the ablation procedure is (recommended dose range is 2-20 mcg/min).

#### • Medication Following AF Ablation Procedure

- It is recommended that physicians follow the relevant recommendations from the 2017 HRS/EHRA/ECAS/APHRS/SOLAECE Expert Consensus Statement on Catheter and Surgical Ablation of AF. All anticoagulation therapy will be recorded on the appropriate case report form.
- All subjects MUST be maintained on systemic oral anticoagulation therapy for 2 months post-procedure. Reinitiate oral anticoagulation therapy within 3-5 hours post procedure.
- Systemic oral anticoagulation is achieved using INR- dose adjusted warfarin (INR should be maintained between 2.0 and 3.0, inclusive), direct thrombin inhibitor, or factor Xa inhibitor.
- At 2 months post-procedure, decision regarding continuation of systemic anticoagulation agents is based on the subject risk for thromo-embolism. Systemic oral anticoagulation is strongly encouraged to be continued beyond 2 months post ablation in subjects with CHADS2 score > 1.

#### 5.15 Antiarrhythmic Drug (AAD) Management

#### 5.15.1 Definitions

• Antiarrhythmic drugs (AADs)

- The study protocol will classify and analyze the following:
  - Class I drugs (e.g., flecainide, propafenone, disopyramide, etc.)
  - Class III drugs (e.g., amiodarone, dronedarone, dofetilide, etc.)

## • Previously Failed AAD

Any AAD that a subject has ever taken for the treatment of his/her AF, prior to enrollment, is considered a "previously failed AAD" if it meets both of the following conditions:

- prior to enrollment, the AAD was ineffective in controlling the subject's AF or produced intolerable side effects leading to its discontinuation;
- o the AAD is administered for AF
- New AAD

ANY AAD that was never taken for the treatment of AF prior to enrollment is considered a "new AAD" if the drug is administered to treat an "atrial tachyarrhythmia" post-enrollment.

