#### 3.1 Subject Selection

#### 3.1.1 Inclusion Criteria

Candidates for this study must meet ALL of the following criteria:

 Symptomatic paroxysmal AF who had at least one AF episode electrocardiographically documented within one (1) year prior to enrollment. Documentation may include electrocardiogram (ECG); Transtelephonic monitoring (TTM), Holter monitor or telemetry strip.

- 2. Failed at least one antiarrhythmic drug (AAD) (class I or III) as evidenced by recurrent symptomatic AF, or intolerable to the AAD.
- 3. Age 18 years or older.
- 4. Signed Patient Informed Consent Form (ICF).
- 5. Able and willing to comply with all pre-, post-, and follow-up testing and requirements.

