#### 4. STUDY ENDPOINTS

#### **4.1 Primary Endpoints**

#### 4.1.1 Primary Effectiveness Endpoint

The primary effectiveness endpoint is defined as the freedom from documented (Symptomatic and asymptomatic) atrial fibrillation, atrial flutter and atrial tachycardia (AF/AFL/AT) (hereinafter collectively referred to as "atrial tachyarrhythmias") recurrence (episodes  $\geq$  30 secs on TTM or continuously recorded on the standard 12-leads ECG or 24 Hour Holter monitoring) during the evaluation period (Day 91-365) and freedom from the following failure modes:

- Acute procedural failure, including:
  - Failure to confirm entrance block in all pulmonary veins post-procedure,
- Repeat ablation failure, including:
  - $\circ$  > 1 repeat ablation procedures during the 3-Month Blanking Period (Day 0-90) after the index ablation procedure.
  - Any repeat ablation procedure during the Evaluation Period.
- DC cardioversion for AF/AFL/AT following the 3-month blanking period
- Surgical treatment for AF/AFL/AT after the index ablation procedure.
- AAD failure: Taking a new AAD, a previously failed AAD at a greater than the highest ineffective historical dose or starting an AAD for AF during the evaluation period (refer to section 5.14 for details).

In summary, effectiveness success is defined as freedom from atrial tachyarrhthmia during the Evaluation Period, off or on a previously failed AAD, and not exceeding 1 repeat ablation procedures for an atrial tachyarrhthmia during the 3-Month Blanking Period.

This study is designed to compare the primary effectiveness of the VISITAG SURPOINT™ Module with EPU to a pre-determined performance goal of 50%, which is indicated as the minimum acceptable success rate at 12 months for a paroxysmal AF population in the 2017 HRS/EHRA/ECAS/APHRS/SOLAECE consensus statement.

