## 7.5 Primary and Secondary Endpoint(s) and Associated Hypotheses

## 7.5.1 **Primary Endpoints and Associated Hypotheses**

## 7.5.1.1 Primary Effectiveness Endpoint

The primary effectiveness endpoint of this study is the effectiveness success rate at Month 12, defined as the proportion of subjects who are freedom from documented (symptomatic and asymptomatic) atrial fibrillation, atrial flutter and atrial tachycardia (AF/AFL/AT) (hereinafter collectively referred to as "atrial tachyarrhythmias") recurrence (episodes  $\geq$  30 secs on TTM or continuously recorded on the standard 12-leads ECG or holter) during the evaluation period (Day 91-365) and freedom from the following failure modes:

- Acute procedural failure, including:
  - Failure to confirm entrance block in all pulmonary veins at the end of procedure
- Repeat ablation failure, including:
  - $\circ$  > 1 repeat ablation procedures during the 3-Month Blanking Period (Day 0-90) after the index ablation procedure.
  - Any repeat ablation procedure during the evaluation period.
- DC cardioversion for AF/AFL/AT following the 3-month blanking period
- Surgical treatment for AF/AFL/AT after the index ablation procedure.
- AAD failure: Taking a new AAD for AF, a previously failed AAD at a greater than the highest ineffective historical dose during the evaluation period.

This study is designed to compare the primary effectiveness of the VISITAG SURPOINTTM Module with EPU to a pre-determined performance goal of 50%, which is indicated as the minimum acceptable success rate at 12 months for a paroxysmal AF population in the 2017 HRS/EHRA/ECAS/APHRS/SOLAECE consensus statement.

The hypotheses to be tested for this evaluation are:

 $H_0: p \le 0.50$  vs.  $H_A: p > 0.50$ ,

where p is the effectiveness success rate.

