#### 5. PRIMARY AND SECONDARY ENDPOINT(S) AND ASSOCIATED HYPOTHESES

#### 5.1 Primary Endpoints and Associated Hypotheses

#### 5.1.1 Primary Effectiveness Endpoint

The primary effectiveness endpoint of this study is the effectiveness success rate at Month 12, defined as the proportion of subjects who are freedom from documented (symptomatic and asymptomatic) atrial fibrillation, atrial flutter and atrial tachycardia (AF/AFL/AT) (hereinafter collectively referred to as "atrial tachyarrhythmias") recurrence (episodes  $\geq$  30 secs on TTM or continuously recorded on the standard 12-leads ECG or holter) during the evaluation period (Day 91-365) and freedom from the following failure modes:

- Acute procedural failure, including:
  - Failure to confirm entrance block in all pulmonary veins at the end of procedure
- Repeat ablation failure, including:
  - > 1 repeat ablation procedures during the 3-Month Blanking Period (Day 0-90) after the index ablation procedure.
  - o Any repeat ablation procedure during the evaluation period.
- DC cardioversion for AF/AFL/AT following the 3-month blanking period
- Surgical treatment for AF/AFL/AT after the index ablation procedure.
- AAD failure: Taking a new AAD for AF, a previously failed AAD at a greater than the highest ineffective historical dose during the evaluation period.

This study is designed to compare the primary effectiveness of the VISITAG SURPOINT Module with EPU to a pre-determined performance goal of 50%, which is indicated as the minimum acceptable success rate at 12 months for a paroxysmal AF population in the 2017 HRS/EHRA/ECAS/APHRS/SOLAECE consensus statement.

The final analyses for primary effectiveness endpoint will apply Bayesian methods and use a beta-binomial model .

The hypotheses to be tested for this evaluation are:

$$H_0: p \le 0.50$$
 vs.  $H_A: p > 0.50$ ,

where p is the effectiveness success rate

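### The AAD-failure rule differs between Protocol 4.1.1 and SAP 5.1.1 and does not clearly score a prior drug that had not failed or was stopped only for intolerance

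*Protocol*

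**What the plan says.** **Eligibility.** Protocol 3.1.1, criterion 2, reads "Failed at least one antiarrhythmic drug (AAD) (class I or III) as evidenced by recurrent symptomatic AF, or intolerable to the AAD". One failed drug is enough, and intolerance qualifies. Other prior drugs may have worked.

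**Drug categories.** Protocol 5.15.1 has two. A previously failed AAD is one taken for AF before enrollment that was ineffective "or produced intolerable side effects leading to its discontinuation". The other is the new AAD: a drug with no earlier use for AF that is given after enrollment for an atrial tachyarrhythmia.

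**Failure rule, Protocol 4.1.1.** AAD failure covers any new AAD and, in addition, "a previously failed AAD at a greater than the highest ineffective historical dose or starting an AAD for AF during the evaluation period". The closing summary of that section describes success as freedom from arrhythmia "off or on a previously failed AAD, and not exceeding 1 repeat ablation procedures" during blanking. For details the section points to 5.14, which covers anticoagulation. The AAD definitions are in 5.15.

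**Failure rule, Protocol 7.5.1.1 and SAP 5.1.1.** Both give AAD failure as "Taking a new AAD for AF, a previously failed AAD at a greater than the highest ineffective historical dose during the evaluation period". Neither has the limb on starting an AAD, and neither repeats the success summary.

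**Elsewhere.** Twelve-month single-procedure success treats any AAD therapy as failure, but it is a secondary endpoint reported descriptively (SAP 5.2, 5.2.1, 9.5). None of the sensitivity analyses in SAP 9.4.4 rescores AAD use.

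**The concern.** Tolerating a previously failed drug during the evaluation period makes sense if the drug is known not to work, because it then cannot explain freedom from AF. That reasoning does not cover two kinds of prior drug:

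- **Kind A:** a drug that may have controlled AF but was stopped only because it was not tolerated.
- **Kind B:** a drug taken before enrollment that had not failed, in a subject who qualified through failure of another drug.

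If a subject stays free of arrhythmia on either kind, the drug may be responsible. In a single-arm comparison with a fixed 50% goal there is no control group in which the same credit would cancel, so any such scoring moves the success rate upward only. The rule in the SAP, which governs the analysis, is the less restrictive of the two.

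**Working it through.** **Step 1. Score each kind under each text.**

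| Prior drug and timing | SAP 5.1.1 / Protocol 7.5.1.1 | Protocol 4.1.1 failure list | Protocol 4.1.1 summary |
|---|---|---|---|
| B, continued from before Day 91 | Not a failure: neither new nor previously failed | Not a failure: nothing is started | Not a success |
| B, started on Day 91–365 | Not a failure | Failure (starting limb) | Not a success |
| A, restarted in blanking and continued | Undetermined: no ineffective dose to compare with | Undetermined, same reason | Allowed as a previously failed drug |
| A, started on Day 91–365 | Undetermined | Failure (starting limb) | Allowed as a previously failed drug |

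Kind B is a conflict between documents and, for a continued drug, a conflict within 4.1.1. Kind A is classified, but its dose limit refers to something that does not exist for that drug.

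**Step 2. Reproduce the plan's power.** Inputs from SAP 8 and 9.4.1:
- 330 enrolled with 10–15% attrition, so n = 330 × 0.90 = 297 or 330 × 0.85 = 280.5, taken as 281
- effectiveness prior Beta(0.01, 0.01), with success if Pr(p > 0.5) > 0.97
- safety prior Beta(1, 1), with success if Pr(q < 0.14) > 0.95
- assumed rates of 65% effectiveness and 8% primary adverse events

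The effectiveness cut-off is the smallest x with Pr(p > 0.5 | Beta(0.01 + x, 0.01 + n − x)) > 0.97.
- n = 281: x = 157 (posterior 0.976; 156 gives 0.968). P(X ≥ 157) is 2.8% at p = 0.50 and 99.9% at p = 0.65.
- n = 297: x = 165 (posterior 0.973; 164 gives 0.964). P(X ≥ 165) is 3.2% at p = 0.50 and 99.97% at p = 0.65.
- Safety: at most 29 of 281 or 31 of 297 events, with power 93.4% and 94.7% at 8%.

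The stated power of more than 90% per endpoint reproduces. This covers the final analysis only. The interim looks are left out, and the simulation appendix is not in the supplied text.

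**Step 3. Sensitivity to the scoring rule.** Let d be the share of subjects counted as successes only because a kind A or kind B drug is not scored as failure. The documents give no value for d, so every value below is an assumption. Two situations are considered:
- The strict rate (such subjects counted as failures) is exactly 50%. The scored rate is then 0.50 + d and the chance of passing is P(X ≥ cut-off | n, 0.50 + d).
- The scored rate is the planned 65%. After strict rescoring, power is P(X ≥ cut-off | n, 0.65 − d).

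| d | Subjects (n = 281 / 297) | Chance of passing, strict rate 50% | Power after rescoring from 65% |
|---|---|---|---|
| 0 | 0 / 0 | 2.8% / 3.2% | 99.9% / 99.97% |
| 1% | 2.8 / 3.0 | 5.8% / 6.5% | 99.8% / 99.9% |
| 2% | 5.6 / 5.9 | 10.7% / 12.1% | 99.4% / 99.6% |
| 5% | 14.1 / 14.9 | 40.8% / 44.7% | 92.9% / 94.7% |
| 10% | 28.1 / 29.7 | 92.9% / 94.7% | 40.8% / 44.7% |

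**Step 4. Margin at the planned rate.** Expected successes minus the cut-off are 0.65 × 281 − 157 = 25.65 (9.1% of subjects) and 0.65 × 297 − 165 = 28.05 (9.4%). About 9% of all subjects would have to be rescored before the expected count fell to the cut-off.

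**The case against.** The case for leaving the plan alone has several parts, and much of it stands.

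- **Kind B is already barred by the protocol.** The 4.1.1 summary admits only subjects off AADs or on a previously failed one. A reader might infer that both kinds escape every version of the rule; the documents do not support that. For kind B, carrying the whole of 4.1.1 into the SAP, summary included, would settle most of it. What remains is the disagreement between the 4.1.1 list and its summary, and the absence of both safeguards from the text to be analysed.
- **Kind A is not proven exempt.** If no dose was ever ineffective, one can read that no dose exceeds the limit or that every dose does. The text does not choose. The path is also narrow under 4.1.1: the drug must have been stopped for side effects, restarted by Day 90 and continued.
- **The figures at 50% are not a demonstrated type I error.** They count every affected subject as a strict failure, although being free of AF on a drug does not prove that the drug caused it. They also use assumed shares at the least favourable true rate.
- **No size can be borrowed from the cited literature.** A reader might take the 130-patient single-centre study in Protocol 1.2, with 104 subjects off AADs, to mean that about 20% are affected. Nothing there says whether the other 26 were on new, ineffective or non-tolerated drugs, so it estimates neither kind.
- **On-drug success is partly visible.** The single-procedure secondary endpoint fails any AAD use. However, it also fails any repeat ablation and is analysed in the Full Set Effectiveness population rather than per protocol, so it does not isolate the effect of the drug rule on the primary result.
- **Counting intolerance as failure is a stated choice.** Removing that exemption outright would change the endpoint and is debatable. The point made here is only that its scoring must be determinate.

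**Conclusion.** The concern holds in limited form. The rule to be analysed scores a subject on a prior drug that had not failed as a success, against the protocol's own success summary. No version determines the score of a drug stopped only for intolerance when it is restarted in blanking and continued. Any resulting bias in the success rate is upward against the 50% goal.

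Its size cannot be derived from the documents. Near the goal, small shares matter: about three subjects (1%) would take the chance of passing from about 3% to 6–7%, and 5% of subjects would take it to 41–45%. Near the planned 65% the conclusion is robust: rescoring 5% leaves 93–95% power. These figures assume the final analysis only, 281 to 297 per-protocol subjects with complete outcomes, and every affected subject rescored as a failure.

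This should be fixed before the analysis, because the score of individual subjects on the primary endpoint depends on which section is read. It does not show that the design is invalid or that type I error control has failed.

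**What to change.** All changes concern endpoint scoring. None alters treatment.

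1. Put one AAD-failure definition in Protocol 4.1.1, Protocol 7.5.1.1 and SAP 5.1.1. Carry over the 4.1.1 limb on starting an AAD. Add that any Class I or III AAD taken for AF, AFL or AT on Day 91–365 that is not a previously failed AAD counts as failure, including one continued from before Day 91.
2. State explicitly how a drug stopped only for intolerance, which has no ineffective dose, is scored.
3. Correct the 4.1.1 cross-reference from section 5.14 to 5.15.
4. Add to SAP 9.4.4 a sensitivity analysis of the primary effectiveness endpoint in the PP population that counts any Class I or III AAD use on Day 91–365 as failure. Record at baseline why each prior AAD failed (ineffective or not tolerated), or that it had not failed.

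**Cost.** Wording in three sections, one extra analysis and a small addition to the baseline drug history. Failed AADs are already recorded before the procedure (Protocol 5.3) and cardiac drugs at each follow-up contact (5.12, Table 5-1). The existing dose limit already requires the highest ineffective dose to be known. The downside is that the observed success rate may be slightly lower.
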